11.3 Tumour response

All patients who meet the eligibility criteria and receive at least 75 % of their first cycle of trial medication and have a baseline assessment of disease will be evaluable for response. To be assigned a status of CR or PR, changes in tumour measurements must be confirmed by repeat measurements performed no less than four weeks after the response criteria are met. To be assigned a status of stable disease (SD), follow-up measurements must have met the SD criteria at least once and at least six weeks after the initial dose of the investigational medicinal product (IMP) AZD3965 is given.

Should rapid tumour progression occur before the completion of 4 weeks, the patient will be classified as having early progression (EP).

Tumour response should be classified as "not evaluable" (NE), only when it is not possible to classify it under another response category, for example, when baseline and/or follow-up assessment is not performed or not performed appropriately.

Expert reviewers appointed by CDD may undertake an independent review of all the Investigator's assessed objective responses (CR and PR). The expert reviewers will include at least one specialist who is not an Investigator in the trial. In case of disagreement between the Investigator's and the expert

reviewers' assessment, discussion will take place between the two parties in order to reach a consensus. However, if it is not forthcoming, the assessment of the expert reviewers will be retained in the clinical study report. The eCRF will reflect the Investigator's opinion.

11.3.1 Recording of response in the eCRF

The applicable overall response category for each visit that includes disease assessment must be recorded in the eCRF, even though the criteria for determination of CR or PR by the protocol must be confirmed after two consecutive observations, no less than four weeks apart.

11.3.2 Other definitions of outcome

Toxic death: Any death to which drug toxicity is thought to have a major contribution.

Early death: Death during the first cycle/28 days of treatment.

12 PATIENT WITHDRAWAL BEFORE COMPLETION OF TREATMENT SCHEDULE

The Investigator must make every reasonable effort to keep each patient on trial for the whole duration of the trial (i.e. until the Off-Study visit 28±7 days after last dose of AZD3965). However, if the Investigator removes a patient from the trial or if the patient declines further participation, final 'Off-Study' assessments should be performed before any therapeutic intervention. All the results of the evaluations and observations, together with a description of the reasons for withdrawal from the trial, must be recorded in the medical records and in the eCRF.

Patients who are removed from the trial due to adverse events (clinical or laboratory) will be treated and followed according to accepted medical practice. All pertinent information concerning the outcome of such treatment must be recorded in the eCRF and on the serious adverse event (SAE) report form where necessary.

The following are justifiable reasons for the Investigator to withdraw a patient from trial.

- AE/SAE
- Withdrawal of consent
- Serious violation of the trial protocol (including persistent patient attendance failure and persistent non-compliance)
- Sponsor's decision to terminate the trial
- Withdrawal by the Investigator for clinical reasons not related to the IMP (AZD3965)
- Evidence of disease progression
- Pregnancy (for female patients during the trial)

For the purposes of this trial a patient who completes six or more treatment cycles is considered to have completed the trial.

13 DEFINING THE END OF TRIAL

The 'end of trial' is defined as the date when the last patient has completed the 'Off-Study' visit or the final follow-up visit (whichever is the later).

It is the responsibility of the CDD to inform the Medicines and Healthcare products Regulations Agency (MHRA) and the Research Ethics Committee (REC) within 90 days of the 'end of the trial' that the trial has closed.

In cases of early termination of the trial (for example, due to toxicity) or a temporary halt by the CDD, the CDD will notify the MHRA and the REC within 15 days of the decision and a detailed, written explanation for the termination/halt will be given.

The entire trial will be stopped when:

- The IMP is considered too toxic to continue treatment before the required number of patients being recruited.
- The stated number of patients to be recruited is reached.
- The stated objectives of the trial are achieved.

Regardless of the reason for termination, all data available for the patient at the time of discontinuation of follow-up must be recorded in the eCRF. All reasons for discontinuation of treatment must be documented.

In terminating the trial, CDD and the Investigators must ensure that adequate consideration is given to the protection of the patient's interest.

14 DATA ANALYSIS AND STATISTICAL CONSIDERATIONS

The final analysis will be conducted after one of the following conditions is met.

- The trial is terminated early (for example, due to toxicity).
- All patients have had the opportunity to receive treatment and have completed their Off-study visit (i.e. 28±7 days after the last dose of AZD3965) or final follow up.

Once one of the conditions is met, a data cut-off date will be established. All patient visits occurring on or before this date will be analysed and summarised in the final clinical study report.

A clinical data cut-off date will be established to allow for primary analysis Clinical Study Report (CSR) reporting once all recruited patients have received up to 12 cycles of AZD3965. The primary analysis CSR will include data from all treated patient visits/assessments up to and including the clinical data cut-off date,

Any patients who continue to receive AZD-3965 in the absence of disease progression or unacceptable toxicity after the clinical data cut-off date will be included in an addendum to the final CSR.

14.1 Presentation of data

Data will be presented in a descriptive fashion. Variables will be analysed to determine whether the criteria for the trial conduct are met. This will include a description of patients who did not meet all the eligibility criteria, an assessment of protocol violations, IMP accountability and other data that impact on the general conduct of the trial.

Baseline characteristics will be summarised for all enrolled patients. Patients who died or withdrew before treatment started or did not complete the required safety observations will be described and evaluated separately.

Treatment administration will be described for all cycles. Dose administration, dose modifications or delays and the duration of therapy will be described.

14.2 Safety

[figure not shown]
Safety data will be collected from the date of written consent. Safety variables will be summarised by descriptive statistics. Laboratory variables will be described using the National Cancer Institute (NCI) Common Terminology Criteria for Adverse Events (CTCAE) Version 4.02.

Adverse events will be reported for each dose level and presented as tables of frequency of AEs by body system and by worse severity grade observed. Tables should indicate related and unrelated events. Laboratory data will be presented by dose level at each observation time. Values outside normal limits will be identified in the listings.

14.3 Pharmacokinetics

Plasma will be separated and analysed to determine the concentrations of AZD3965 using a previously developed LCMS method. Parameters to be calculated will include: area under the plasma concentration-time curve (AUC_{0-t}), maximum concentration achieved (C_{max}), time to maximum concentration (T_{max}) and elimination half-life ($T_{1/2}$) for AZD3965.

At the end of the trial when all the data has been analysed, a full PK report will be produced for inclusion in the final clinical study report.

14.5 Anti-tumour activity

Documenting anti-tumour activity is a secondary objective of this trial. Patients must receive at least 75% of their first cycle of the trial medication to be evaluable for response. Objective responses, the best tumour response achieved by each patient while on trial and the time to progression will be presented in the data listings.

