1.2.2 Secondary objectives and endpoints

Secondary Objectives	Endpoints
1. To investigate the pharmacokinetic (PK) behaviour of AZD3965 in patients with advanced cancer	1. Determining the plasma levels of AZD3965 after single and multiple doses of AZD3965.
2. Part 2: To assess the potential anti-tumour activity of AZD3965 in patients with relapsed or refractory diffuse large B cell Lymphoma (DLBCL) and/or Burkitt Lymphoma (BL)	2. Objective response: stable disease (SD), partial response (PR), or complete response (CR) according to Response Criteria Evaluation (RECIST, version 1.1) or International Working Group criteria for Lymphoma (see appendix 2A and 2B).

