1.2.3 Tertiary objectives and endpoints

1.3 Design

This is a multi-centre, dose escalation, Phase I trial in two parts.

In Part 1 each patient cohort included up to six evaluable patients following a rolling six dose escalation scheme (Skolnik A.M. *et al.*, 2008) of AZD3965 until a recommended Phase II dose (RP2D) and/or the maximum tolerated dose (MTD) was defined.

42 patients with advanced solid tumours or Lymphoma were entered into Part 1. The final number depended on the number of dose escalations required to reach MTD or the tolerated dose at which monocarboxylate transporter 1 (MCT1) was inhibited. A RP2D was proposed from the safety and pharmacokinetic (PK) results from Part 1.

All patients in Part 2 will be treated at this RP2D to further explore the tolerability of this dose and schedule and to explore proof of principle of MCT1 inhibition in tumour types that were shown to express high MCT1 and low monocarboxylate transporter 4 (MCT4) or in which AZD3965 showed some effect pre-clinically.

In Part 2 there will be up to 20 evaluable patients entered with relapsed or refractory diffuse large B cell Lymphoma (DLBCL) and Burkitt Lymphoma (BL).

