3.2 Patient evaluability

Part 1:

All patients that met the eligibility criteria and take at least one dose of AZD3965 were evaluable for safety decisions.

[figure not shown]
Patients who received less than 75% of their first continuous treatment cycle (for reasons other than toxicity) would not be evaluable for dose escalation decisions. Patients who completed 75% of their first continuous treatment cycle but did not complete the end of Cycle 1 ERG and ophthalmology assessments could also not be evaluable for dose escalation decisions. This was discussed on a per patient basis between the Investigator, Chief Investigator (CI) and CDD.

Part 2:

All patients that meet the eligibility criteria and take at least one dose of AZD3965 will be evaluable for safety decisions.

All patients who meet the eligibility criteria and take at least 75% of their first continuous treatment cycle (28 days) of AZD3965 and have a baseline assessment of disease will be evaluable for response.

To be assigned a status of complete response (CR) or partial response (PR), changes in tumour measurements must be confirmed by repeat measurements performed no less than four weeks after the response criteria are met. To be assigned a status of stable disease (SD), follow-up measurements must have met the SD criteria at least once and at least six weeks after the initial dose of the IMP AZD3965 is given.

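### Part 2 response is confined to patients who took at least 75% of cycle 1, early drop-outs are replaced, and section 14.5 adds no all-dosed denominator; objective response is also defined in two ways

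*Protocol*

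**What the plan says.** Anti-tumour activity is the one efficacy objective visible for Part 2. Section 1.2.2 words it as "Part 2: To assess the potential anti-tumour activity of AZD3965 in patients with relapsed or refractory diffuse large B cell Lymphoma" (Burkitt lymphoma is also included), and section 14.5 confirms its rank: "Documenting anti-tumour activity is a secondary objective of this trial". The sample is limited in section 1.3: "In Part 2 there will be up to 20 evaluable patients entered".

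**Output.** Section 14.5 names listings: objective responses and "best tumour response achieved by each patient while on trial and the time to progression will be presented in the data listings". Section 14.1 adds only the general rule, "Data will be presented in a descriptive fashion". Section 14.2, by contrast, commits the safety data to summary statistics and frequency tables.

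**Who counts for response.** Section 3.2 requires that Part 2 patients be eligible and "take at least 75% of their first continuous treatment cycle (28 days) of AZD3965 and have a baseline assessment of disease". Section 11.3 repeats this, and section 14.5 restates the 75% condition.

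**Who is replaced.** Section 5.7.1 replaces a Part 2 patient who misses more than a quarter of cycle 1, unless the cause is drug-related toxicity.

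**Early failures.** Section 11.3 has a class for rapid progression within the first 4 weeks, and section 11.3.2 defines early death as death in the first cycle.

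**The endpoint.** Section 1.2.2 gives "Objective response: stable disease (SD), partial response (PR), or complete response (CR", and section 3.1.2 agrees. Section 11.3, describing the independent review, uses objective responses for CR and PR only.

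**The concern.** Taken separately, the evaluability rule and the replacement rule are both common in Phase I. Together they select patients on something that happens after dosing starts and is related to outcome. A patient whose lymphoma progresses in the second week, or who dies then of disease, has not taken 75% of the cycle. That patient is outside the response set, and the place goes to someone else. Only patients who stayed well enough for about three weeks of dosing remain in the denominator.

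Section 14.5 names no second denominator that would show the effect. At up to 20 patients, a few exclusions change the reported proportion visibly, and readers will use that proportion to judge whether the drug is active in these lymphomas.

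The two meanings of objective response add a separate risk. Under sections 1.2.2 and 3.1.2 a patient with stable disease is an objective response. Under section 11.3 that patient is not. Section 14.5 uses the term without choosing.

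**Working it through.** The protocol states no response rate, target or interval for Part 2, so there is no figure to reproduce. The check follows the rules as written and then sizes the effect.

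**Step 1: the threshold.** 75% of a 28-day cycle is 0.75 × 28 = 21 days of dosing. Stopping earlier puts a patient below the evaluability limit in 3.2, 11.3 and 14.5, and above the missed-dose limit in 5.7.1.

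**Step 2: what happens to each kind of early stop.**

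| Event before day 21 | In response set (3.2, 11.3, 14.5)? | Replaced (5.7.1)? |
|---|---|---|
| Stops for progression | No | Yes |
| Dies, not drug-related | No | Yes |
| Stops for drug toxicity | No | Not under this criterion |

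The first two are the early failures for which 11.3 and 11.3.2 provide categories.

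**Step 3: can such patients be responders?** The first scheduled disease assessment is at the end of cycle 2 (section 8.4), and CR or PR must be confirmed at least four weeks later (sections 3.2 and 11.3). A patient who progressed or died in the first three weeks cannot meet that. Zero responses is therefore the natural count for them. It is an assumption for patients who missed doses for other reasons and continued.

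**Step 4: size.** Let x be responders, 20 the evaluable patients (the maximum in 1.3, read here as response-evaluable), and k the dosed but non-evaluable patients, with no responses among them.

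- Evaluable proportion: x/20. All-dosed proportion: x/(20 + k). Their ratio is (20 + k)/20.
- Exact (Clopper-Pearson) 95% limits for x of n: lower = the 2.5% point of Beta(x, n − x + 1); upper = the 97.5% point of Beta(x + 1, n − x).

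With x = 4 (an assumption):

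| k | Dosed | Proportion | Exact 95% CI | Evaluable ÷ all-dosed |
|---|---|---|---|---|
| 0 | 20 | 20.0% | 5.7% to 43.7% | 1.00 |
| 2 | 22 | 18.2% | 5.2% to 40.3% | 1.10 |
| 5 | 25 | 16.0% | 4.5% to 36.1% | 1.25 |
| 8 | 28 | 14.3% | 4.0% to 32.7% | 1.40 |

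**Step 5: the endpoint wording.** With 4 CR or PR and 6 SD among 20 (assumed counts), the section 11.3 meaning gives 4/20 = 20% (5.7% to 43.7%). The section 1.2.2 meaning gives 10/20 = 50% (27.2% to 72.8%).

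**The case against.** The strongest reply is that section 14.5 describes listings and nothing more. It does not say that responses will only be listed. Section 15.5 puts all clinical data on listings and builds the study report from them, and section 14.1 allows descriptive summaries. The interval method, the summary tables, and the start, event and censoring rules for time to progression commonly belong in a statistical analysis plan, which is not shown. This stands. A reader might infer from 14.5 that a response rate is ruled out, but the text does not support that.

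Three other inferences also fail. The protocol does give a denominator: the evaluable set is defined in 3.2, 11.3 and 14.5. It does not say that deaths are left out of time to progression; it leaves that variable undefined. And time to progression is a recognised endpoint, so replacing it with progression-free survival would be a preference and not a correction.

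It can also be said that section 11.3 reserves the not-evaluable class for patients who fit no other category and gives rapid progressors their own class, which suggests they are meant to be seen. They may well appear in a listing. But the same section opens by limiting response evaluability to the 75% group, so it does not put them in the denominator.

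Finally, this is a secondary objective of a Phase I trial with no efficacy test or threshold in the visible text, and a full listing lets a reader count. That limits the severity. It does not remove the selection built into the evaluable set.

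**Conclusion.** The point holds as a low to moderate one. The stated evaluability and replacement rules, taken together, remove patients who progress or die early in cycle 1 from the response set and refill their places. Any proportion taken from that set is then biased upward by the factor (20 + k)/20 if none of the k excluded patients respond: 1.10 for 2 exclusions, 1.25 for 5 and 1.40 for 8. In the illustration, 20% becomes 16% with 25 dosed. The intervals overlap heavily, so the gain is an honest denominator and not better precision.

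The sizes rest on assumed counts of responders and exclusions and on reading the 20 as response-evaluable patients. The direction does not depend on the counts, provided that at least one patient responds and excluded patients respond less often than those retained.

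The conflict over whether stable disease is an objective response is an inconsistency within the protocol, whatever an analysis plan may add. The verdict does not extend to a claim that the protocol forbids a summary, lacks a denominator or mishandles deaths in time to progression.

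**What to change.** Add to section 14.5 that, for Part 2, the number and proportion of patients with confirmed CR or PR will be reported with an exact (Clopper-Pearson) 95% CI in two sets side by side:

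- all patients who took at least one dose, with early progression, early death and not evaluable counted as non-responders;
- the response-evaluable set as already defined.

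Show stable disease as its own count, and give the number of dosed patients outside the evaluable set with the reason for each. Keep the listings as support. Align the endpoint wording in 1.2.2 and 3.1.2 with 11.3 so that objective response means CR or PR and stable disease is named separately.

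The evaluability and replacement rules can stay as they are. The cost is one paragraph, a wording edit in two tables of objectives, and one results table from data already collected. No extra patients or procedures are needed.

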14.6 Exploratory work

This trial is conducted under a clinical trial authorisation (CTA) and approval from the Medicines and Healthcare products Regulations Agency (MHRA) and the relevant Research Ethics Committee(s) will be obtained before the start of this trial. This trial is sponsored and monitored by the CRUK CDD. Applicable regulatory requirements are described in this section.

15.1 Protocol deviations and amendments

Do not deviate from the protocol unless approval has been obtained from the CDD.

Amendments to the protocol may only be made with the approval of the CDD. A protocol amendment may be subject to review by the assigned Ethics Committee, HRA and the MHRA. Written documentation of the Ethics Committee and HRA (and if appropriate the MHRA) 'favourable opinion' (i.e. approval) must be received before the amendment can be implemented and incorporated into the protocol if necessary.

15.2 Completion of the electronic case report form (eCRF)

Electronic CRFs approved by the CDD will be used to collect the data. The Investigator is responsible for ensuring the accuracy, completeness, clarity and timeliness of the data reported in the eCRFs.

Only the Investigator and those personnel who have signed the Delegation Log provided by the CDD and have been authorised by the Investigator should enter or change data in the eCRFs. Authorised

users will be included on a User Management Tool Form in order to be provided access to the eCRF. All protocol required investigations must be reported in the eCRF. The Investigators must retain all original reports, traces and images from these investigations for future reference.

Data will be entered directly into electronic screens by authorised site personnel. Amendments to eCRF data will be made directly to the system and the system audit trail will retain details of the original value(s), who made the change, a date and time, and a reason for the change.

Once an eCRF form has been entered by the site personnel, the data are cleaned using manual and automated checks. Queries will be issued electronically to the site. Authorised personnel must answer the queries by making relevant amendments to data or providing a response. Answered queries will be closed or reissued as appropriate.

Once the patient is 'off study' and the eCRF has been fully completed, the Investigator must provide an electronic signature to authorise the complete subject casebook.

At the end of the trial all eCRFs are retained and archived by the CDD and a PDF copy provided to the Investigator who is responsible for archiving at site.

15.3 Trial performance and monitoring

Before the trial can be initiated, the prerequisites for conducting the trial must be clarified and the organisational preparations made with the trial centre. CDD must be informed immediately of any change in the personnel involved in the conduct of the trial.

During the trial the CDD Clinical Research Associate (CRA) is responsible for monitoring data quality in accordance with CDD's standard operating procedures (SOPs). Before the trial start, the Investigator will be advised of the anticipated frequency of the monitoring visits. The Investigator will receive reasonable notification before each monitoring visit.

It is the responsibility of the CRA to:

- review trial records and compare them with source documents;
- check pharmacokinetic and pharmacodynamic samples and storage;
- discuss the conduct of the trial and the emerging problems with the Investigator;
- check that the drug storage, dispensing and retrieval are reliable and appropriate; and
- verify that the available facilities remain acceptable.

All the unused drug supplied must be returned to the supplier, or if authorised by Cancer Research UK properly destroyed at the Investigator site by an authorised person who will provide signed confirmation.

It is the responsibility of the Sponsor to inform the Main REC within 90 days of the 'end of the trial' that the trial has closed (see definition in Section 13).

